## 14 APPENDICES

# 14.1 Appendix 1: List of concomitant medications

In general, the use of any concomitant medication deemed necessary for the care of the patient is permitted in this study, except as specifically prohibited below. Combination administration of study drugs could result in drug-drug interactions (DDI) that could potentially lead to reduced activity or enhanced toxicity of the concomitant medication and/or BGJ398.

Confidential

The following lists in Table 15 are based on the Indiana University School of Medicine's "Clinically Relevant" Table (Flockhart TableTM; Flockhart 2007) and supplemented with the FDA Draft guidance and the online database Drugbank.ca. Note: this may not be an exhaustive list of medications, investigator should use this list as a guide.

Table 15: Drugs to be used with caution while on study

Category	Drug Names	
CYP3A substrates with narrow therapeutic index	alfentanil, cyclosporine, diergotamine, dihydroergotamine, ergotamine, fentanyl, sirolimus, tacrolimus, terfenadine, warfarin sodium or any other coumadin-derivative anticoagulants, direct thrombin inhibitors (eg, argatroban), and Factor Xa inhibitors (eg, rivaroxaban)	
Moderate inhibitors of CYP3A4	amprenavir, aprepitant, atazanavir, cannabinoids, casopitant, cimetidine, ciprofloxacin, darunavir, diltiazem, fosamprenavir, imatinib, metronidazole, Schisandra sphenanthera, sertraline, suboxone, tofisopam, verapamil, zafirlukast	
Moderate inducers of CYP3A4	bosentan, cotrimoxazole, efavirenz, etravirine, ethosuximide, genistein, metyrapone, mexiletine, modafinil, nafcillin, talviraline, tipranavir	
Medications which alter the pH of the GI tract a,b	antacids, H 2 antagonists (eg, ranitidine), proton-pump inhibitors (eg, omeprazole)	
Medications that have possible risk of TdP/QT prolongation		
Medications that have conditional risk of TdP/QT prolongation	amitriptyline, amisulpride, ciprofloxacin, clomipramine, desipramine, diphenhydramine, doxepin, fluoxetine, galantamine, imipramine, nortriptyline, paroxetine, protriptyline, sertraline, solifenacin, trazodone, trimethoprimsulfa, trimipramine	

Category	Drug Names

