# 14.2 Appendix 2: List of prohibited medications

Table 16: List of prohibited medications and substances while on study

Category	Drug name
Strong inhibitors of CYP3A4	clarithromycin, conivaptan, fluconazole, fluvoxamine, indinavir, itraconazole, ketoconazole, lopinavir, mibefradil, miconazole, nefazodone, nelfinavir, norfloxacin, posaconazole, ritonavir, saquinavir, telithromycin, voriconazole
	grapefruit, grapefruit juice, grapefruit hybrids, pomegranates, star fruits, pomelos, Seville oranges or products containing juice of these fruits
Strong inducers of CYP3A4	avasimibe, carbamazepine, nevirapine, phenobarbital, phenytoin, pioglitazone, primidone, rifabutin, rifampin, St. John's wort, troglitazone
Medications which increase serum phosphorus and/or calcium	calcium, parathyroid hormone, phosphate, vitamin D (including multivitamins containing vitamin D)

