2.4 Protocol Deviations

Unless otherwise specified, the FAS will be used for the protocol deviation summary tables and listing. The number (%) of patients with any CSR-reportable protocol deviation will be tabulated by the deviation category as listed below:

- Subject enrolled and did not satisfy the entry criteria
- Subject developed study/treatment withdrawal criteria during the study, but was not withdrawn
- Subject received the wrong treatment or incorrect dose
- Subject took a prohibited concomitant medication
- Major procedural or other GCP deviation that potentially affects patient safety or efficacy data interpretation

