5.10 CYP3A4 Inhibitors and Inducers

The list of CYP3A4 inducers and inhibitors are retrieved from the Drug Bank ([Wishart 2017](#)). Terms are coded based on WHODrug Enhanced + Herbals (HD/DDE) Mar2018 B3 global.

The coded concomitant medications which contained below preferred terms will be marked according to type (inhibitor/inducer) and category (moderate/strong) with the exception that medication administered through topical, optic or aural routes will not be considered as inducers or inhibitors.

| Type | Category | Preferred Name/Generic Name | Type | Category | Preferred Term |
|-----------|----------|-----------------------------|---------|----------|----------------|
| Inhibitor | Moderate | AMIODARONE | Inducer | Moderate | AVASIMIBE |
| Inhibitor | Moderate | AMPRENAVIR | Inducer | Moderate | BEXAROTENE |
| Inhibitor | Moderate | ANASTROZOLE | Inducer | Moderate | BOSENTAN |
| Inhibitor | Moderate | APREPITANT | Inducer | Moderate | DABRAFENIB |
| Inhibitor | Moderate | BARNIDIPINE | Inducer | Moderate | EFAVIRENZ |
| Inhibitor | Moderate | BENIDIPINE | Inducer | Moderate | ETRAVIRINE |
| Inhibitor | Moderate | CLOBAZAM | Inducer | Moderate | MIFEPRISTONE |
| Inhibitor | Moderate | CLOZAPINE | Inducer | Moderate | MODAFINIL |
| Inhibitor | Moderate | CRIZOTINIB | Inducer | Moderate | NAFCILLIN |
| Inhibitor | Moderate | DANAZOL | Inducer | Strong | APALUTAMIDE |
| Inhibitor | Moderate | DESVENLAFAZINE | Inducer | Strong | CARBAMAZEPINE |
| Inhibitor | Moderate | DILTIAZEM | Inducer | Strong | DEXAMETHASONE |
| Inhibitor | Moderate | DIMETHYL SULFOXIDE | Inducer | Strong | ENZALUTAMIDE |
| Inhibitor | Moderate | DRONEDARONE | Inducer | Strong | FOSPHENYTOIN |
| Inhibitor | Moderate | ERYTHROMYCIN | Inducer | Strong | LUMACRAFTOR |

| Type | Category | Preferred Name/Generic Name | Type | Category | Preferred Term |
|-----------|----------|-----------------------------|---------|----------|----------------------|
| Inhibitor | Moderate | FLUCONAZOLE | Inducer | Strong | MIDOSTAURIN |
| Inhibitor | Moderate | FLUVOXAMINE | Inducer | Strong | MITOTANE |
| Inhibitor | Moderate | FOSAMPRENAVIR | Inducer | Strong | NEVIRAPINE |
| Inhibitor | Moderate | FOSNETUPITANT | Inducer | Strong | OXCARBAZEPINE |
| Inhibitor | Moderate | FUSIDIC ACID | Inducer | Strong | PENTOBARBITAL |
| Inhibitor | Moderate | HALOPERIDOL | Inducer | Strong | PHENOBARBITAL |
| Inhibitor | Moderate | IMATINIB | Inducer | Strong | PHENYTOIN |

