| Inhibitor | Moderate | INDALPINE | Inducer | Strong | PRIMIDONE |
| Inhibitor | Moderate | ISAVUCONAZOLE | Inducer | Strong | RIFAMPICIN |
| Inhibitor | Moderate | ISAVUCONAZONIUM | Inducer | Strong | RIFAMYCIN |
| Inhibitor | Moderate | ISONIAZID | Inducer | Strong | RIFAXIMIN |
| Inhibitor | Moderate | ISRADIPINE | Inducer | Strong | RIMEXOLONE |
| Inhibitor | Moderate | LINAGLIPTIN | Inducer | Strong | HYPERICUM PERFORATUM |
| Inhibitor | Moderate | LOVASTATIN | Inducer | Strong | GLUCOCORTICOIDS |
| Inhibitor | Moderate | LULICONAZOLE | | | |
| Inhibitor | Moderate | MICONAZOLE | | | |
| Inhibitor | Moderate | MIFEPRISTONE | | | |
| Inhibitor | Moderate | MILNACIPRAN | | | |
| Inhibitor | Moderate | NETUPITANT | | | |
| Inhibitor | Moderate | NICARDIPINE | | | |
| Inhibitor | Moderate | NILVADIPINE | | | |
| Inhibitor | Moderate | PAROXETINE | | | |
| Inhibitor | Moderate | PRIMAQUINE | | | |
| Inhibitor | Moderate | RISPERIDONE | | | |
| Inhibitor | Moderate | SERTRALINE | | | |
| Inhibitor | Moderate | SIMEPREVIR | | | |
| Inhibitor | Moderate | TIOCONAZOLE | | | |
| Inhibitor | Moderate | VENETOCLAX | | | |
| Inhibitor | Moderate | VENLAFAXINE | | | |
| Inhibitor | Moderate | VERAPAMIL | | | |
| Inhibitor | Moderate | ZIMELDINE | | | |
| Inhibitor | Moderate | ZIPRASIDONE | | | |
| Inhibitor | Strong | ATAZANAVIR | | | |
| Inhibitor | Strong | BOCEPREVIR | | | |
| Inhibitor | Strong | CLARITHROMYCIN | | | |
| Inhibitor | Strong | CLOTRIMAZOLE | | | |
| Inhibitor | Strong | COBICISTAT | | | |
| Inhibitor | Strong | CONIVAPTAN | | | |

| Type | Category | Preferred Name/Generic Name | Type | Category | Preferred Term |
|-----------|----------|-----------------------------|------|----------|----------------|
| Inhibitor | Strong | CURCUMIN | | | |
| Inhibitor | Strong | DANOPREVIR | | | |
| Inhibitor | Strong | DARUNAVIR | | | |
| Inhibitor | Strong | DELAVIRDINE | | | |
| Inhibitor | Strong | DILTIAZEM | | | |
| Inhibitor | Strong | ECONAZOLE | | | |
| Inhibitor | Strong | EFAVIRENZ | | | |
| Inhibitor | Strong | ELVITEGRAVIR | | | |
| Inhibitor | Strong | ERGOTAMINE | | | |
| Inhibitor | Strong | IDEALISISB | | | |
| Inhibitor | Strong | INDINAVIR | | | |
| Inhibitor | Strong | ITRACONAZOLE | | | |
| Inhibitor | Strong | KETOCONAZOLE | | | |
| Inhibitor | Strong | LOPERAMIDE | | | |
| Inhibitor | Strong | LOPINAVIR | | | |
| Inhibitor | Strong | MIBEFRADIL | | | |
| Inhibitor | Strong | MIDOSTAURIN | | | |
| Inhibitor | Strong | NALOXONE | | | |

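### SAP 5.10 lists diltiazem as both a moderate and a strong CYP3A4 inhibitor and differs from the protocol's strength lists, so the TEAE subgroups by CYP3A4 strength are not exclusive or aligned

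*SAP*

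**What the plan says.** SAP Section 2.2.8 says the TEAE summaries will be repeated by CYP3A4 exposure in three groups (strong, moderate, none), once for inhibitors and once for inducers. The efficacy subgroups in the same section are only optional. Group membership comes from SAP Section 5.10, where a coded concomitant medication matching a listed name "will be marked according to type (inhibitor/inducer) and category (moderate/strong"). The only exception concerns route: "medication administered through topical, optic or aural routes will not be considered as inducers or inhibitors".

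Diltiazem has two inhibitor rows in that list, "Inhibitor | Moderate | DILTIAZEM" and "Inhibitor | Strong | DILTIAZEM".

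The protocol has its own strength lists. Appendix 1 (Table 15, use with caution) gives the moderate inhibitors, beginning "amprenavir, aprepitant, atazanavir, cannabinoids, casopitant, cimetidine, ciprofloxacin, darunavir, diltiazem". Appendix 2 (Table 16, prohibited) gives the strong inhibitors, beginning "clarithromycin, conivaptan, fluconazole, fluvoxamine, indinavir", and the strong inducers. The SAP instead has "Inhibitor | Moderate | FLUCONAZOLE".

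SAP Section 2.4 tabulates a separate deviation category, "Subject took a prohibited concomitant medication". SAP Section 4 records no change from the protocol-specified analyses.

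**The concern.** A three-way split by highest exposure should place each patient in exactly one group. With diltiazem in both strength lists and no precedence rule in 2.2.8 or 5.10, the programmer must either count a diltiazem user in both groups or choose one without a pre-specified basis.

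The disagreement with the protocol raises a second problem. Protocol Section 6.3.2 describes the study drug as a CYP3A4 substrate, so a reader will use these tables to see whether inhibitor or inducer use goes with a different adverse event profile. If strong means one thing in the protocol and another in the SAP, the tables cannot be read against the protocol's cautions and prohibitions. A patient who took systemic fluconazole would be a prohibited strong-inhibitor user in the deviation table and a moderate-inhibitor user in the TEAE table, with nothing to tell the reader why.

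**Working it through.** The plan states no figure to reproduce. The check compares the lists drug by drug.

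**Inputs.** SAP 5.10 has 47 moderate and 38 strong inhibitors, and 9 moderate and 20 strong inducers. Protocol Table 15 has 18 moderate inhibitors and 12 moderate inducers. Protocol Table 16 has 18 strong inhibitors (leaving aside the fruit entries) and 11 strong inducers. Rifampin was matched to rifampicin, and St. John's wort to Hypericum perforatum.

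**Step 1: duplicates within SAP 5.10.** Among inhibitors, exactly one drug has both strengths: diltiazem. Among inducers there is none. Efavirenz, midostaurin and mifepristone appear both as inhibitor and as inducer. That is not a conflict, because the two types are summarised separately.

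**Step 2: SAP against protocol.**

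| Drug | Type | Protocol | SAP 5.10 |
|---|---|---|---|
| diltiazem | inhibitor | moderate (Table 15) | moderate and strong |
| fluconazole, fluvoxamine, miconazole | inhibitor | strong, prohibited (Table 16) | moderate |
| avasimibe | inducer | strong, prohibited (Table 16) | moderate |
| atazanavir, darunavir | inhibitor | moderate (Table 15) | strong |
| norfloxacin | inhibitor | strong, prohibited (Table 16) | not listed |
| pioglitazone, rifabutin, troglitazone | inducer | strong, prohibited (Table 16) | not listed |

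**Step 3: counts.**
- Table 16 inhibitors: 18 = 14 strong in the SAP + 3 moderate + 1 absent.
- Table 16 inducers: 11 = 7 strong + 1 moderate + 3 absent.
- Together, 8 of the 29 prohibited CYP3A4 drugs (18 + 11) do not carry the strong flag: 4 are moderate and 4 are unlisted. A patient whose only relevant drug is one of the unlisted four counts as having received none of that type.
- Table 15 inhibitors: 18 = 6 moderate only + 3 strong (one of them diltiazem, also moderate) + 9 absent.
- Table 15 inducers: 12 = 5 moderate + 0 strong + 7 absent. One of the absent seven, tipranavir, appears in the SAP as a strong inhibitor.

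**Step 4: overlap beyond diltiazem.** Removing one diltiazem row would not make the groups exclusive. A patient who takes one strong and one moderate inhibitor still qualifies for both, because neither section says that the highest strength decides.

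**The case against.** Four objections carry weight.

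*The lists have different sources and purposes.* The SAP list comes from DrugBank. The protocol's Table 15 rests on the Flockhart table, supplemented by FDA draft guidance and DrugBank, and is offered as a non-exhaustive guide for investigators. One list governs conduct and the other codes an analysis variable, so they need not be identical. This stands as a possible explanation of the strength differences. It cannot explain one drug with two strengths inside one SAP table, and SAP Section 4 does not mention the difference.

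*Deviations are still caught.* A reader might infer that fluconazole becomes a permitted drug in the analysis. The documents do not support that. Protocol Section 6.3 makes a drug prohibited if it is on any prohibited list, SAP 2.4 tabulates such use, and nothing links the deviation check to 5.10. The flag in 5.10 assigns a strength and grants no permission.

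*The strong group may not be small.* A reader might infer that it must be, since strong inhibitors are prohibited, and that a few misplaced patients would therefore dominate it. That assumes SAP-strong equals protocol-prohibited. SAP-strong inhibitors include loperamide and clotrimazole, neither of them in Table 16. The protocol recommends antidiarrhoeal medication early (Table 5 and Section 6.3.1) and names clotrimazole lozenges in Table 6. SAP-strong inducers include dexamethasone, which Table 6 recommends as a mouth rinse. Whether lozenges and rinses fall under the topical exception is unclear. No usage counts are given, so the group could be small or large.

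*A rule may exist elsewhere.* SAP Section 1 places derived-variable specifications in the ADaM Reviewer's Guide, which is not among the documents. A precedence rule could be there, so double counting follows from the SAP as written but is not shown to occur in the outputs. The route exception also removes topical miconazole, though not the other drugs.

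**Conclusion.** The point holds as a minor defect. One drug is in two groups meant to be exclusive, six others change strength between the documents, and four prohibited drugs are missing from the SAP list. No highest-strength rule is stated in the SAP.

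The reach is limited to descriptive TEAE subgroup tables. ORR, the sample size and the Cohort 3 expansion decision do not depend on 5.10. How many patients are affected, and how large the strong group is, cannot be judged from the documents. Nor do the documents settle which strength is pharmacologically right for any drug; the conclusion is only that the lists must be reconciled or their difference explained. It rests on the two diltiazem rows being in the source table. Both rows are intact, in separate blocks of the list, so a fault in reading the table is unlikely.

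**What to change.** Change the SAP only:

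1. In Section 5.10, give each drug one strength per type, which leaves one inhibitor row for diltiazem.
2. In Section 2.2.8, assign each patient to the highest strength received, separately for inhibitors and inducers, so that the three groups are exclusive.
3. Reconcile 5.10 with protocol Tables 15 and 16, covering the six strength differences and the four missing prohibited drugs. Otherwise, state in SAP Section 4 that the analysis list deliberately differs, and why.

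The cost is a short SAP amendment and a matching edit to the derived-variable specification, best made before the affected tables are produced. The protocol's prohibited-medication list need not change. Rewriting Appendices 1 and 2 would be a protocol amendment needing the approvals in protocol Section 12.1 and would touch a concomitant-medication rule; this point does not call for that.

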5.11 Phosphate Binders

All terms in the search strategy are based on WHODrug Enhanced + Herbals (HD/DDE)
Mar2018 B3 Global.

| Preferred Name/Generic Name | Preferred Name/Generic Name | Preferred Name/Generic Name |
|-------------------------------|-----------------------------|-----------------------------|
| CALCIUM CARBONATE | SEVELAMER HYDROCHLORIDE | ALUMINUM HYDROXIDE |
| CALCIUM POLYSTYRENE SULFONATE | SUCROFERRIC OXYHYDROXIDE | |
| SEVELAMER | FERRIC CITRATE | |
| SEVELAMER CARBONATE | LANTHANUM CARBONATE | |

